### **7.5. Recording and Evaluating Adverse Events and Serious Adverse Events**

It is the responsibility of the Investigator to collect all adverse events (AEs), serious and non-serious, derived by spontaneous, unsolicited reports of subjects, by observation and by routine open questionings e.g., "How have you felt since I last saw you?"

For randomized and enrolled patients, AEs will be captured from the time of signing of Informed Consent Form until End of Study or Early Termination. Adverse events/ Serious Adverse Events (SAEs) should be followed to resolution, stabilization, or until 30 days after the last dose of the study drug upon which patients will be referred to their primary medical provider for follow-up.

All adverse events, including observed or volunteered problems, complaints, or symptoms, are to be recorded on the appropriate eCRF.

Subjects should be instructed to report any adverse event that they experience to the Investigator, after signing the Informed Consent. Investigators should make an assessment for adverse events at each visit and record the event on the appropriate adverse event eCRF.

Pre-existing conditions will be recorded in the subject's source record and eCRF on the Medical History or appropriate page.

A treatment-emergent AE (TEAE) will be defined as an AE that begins or that worsens in severity after at least one dose of study drug has been administered.

Clinically significant abnormal laboratory or other examination (e.g., ECG) findings that are detected during the study or are present at baseline and significantly worsen during the study should be reported as adverse events.

The Investigator will exercise his or her medical and scientific judgment in deciding whether an abnormal laboratory finding or other abnormal assessment is clinically significant. Significant abnormal laboratory values occurring during the clinical study will be followed until repeat tests return to normal, stabilize, or are no longer clinically significant. The Investigator will attempt to establish a diagnosis of the event on the

basis of signs, symptoms, or other clinical information. In such cases, the diagnosis, not the individual signs or symptoms, should be documented as the AE or SAE.

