Demographic variables include age, sex, race, and ethnicity. Baseline characteristics will include weight (kg) and BMI (kg/m²) as well as the qualifying (baseline) NPRS and 4-point categorical pain intensity scores. Demographics and baseline characteristics will be presented in a by-subject listing and summarized overall and by treatment group for the Safety population and the mITT population, if they differ.

6.2 **Medical History**

Medical history, as collected at screening, will be coded using the Medical Dictionary for Regulatory Activities (MedDRA) version 21.0 and summarized by system organ class (SOC) and preferred term (PT) in a frequency table based on the safety population. The SOC and PT will each be sorted in descending order by overall frequency. Medical histories will also be presented in a by-subject listing using the coded and verbatim history terms.

AEs that occur prior to treatment or that are related to a medical history event will be captured as medical history prior to database lock.

6.3 **Prior and Concomitant Medication**

Prior medications/therapies are those that stop prior to the start of the study medication administration. Any medication/therapy that stops at or after the date and time of start of treatment or those with missing stop dates are considered concomitant medication/therapy. Surgical medications/Anesthesia used during and immediately after surgery will be listed but will not be summarized.

Prior and concomitant medications are collected at screening, and updated throughout the study as needed. Prior and concomitant medications will be coded using the March 1, 2018 version of the WHODrug. Subjects who take concomitant medications will be presented in a by-subject listing of verbatim and coded terms and summarized by drug class and preferred name, overall and by treatment group, for the safety population.

A by subject listing of all prior and concomitant medications will be presented with Surgical medications/Anesthesia used during surgery identified. Additionally, a summary and by-subject listing of concomitant medications that were prescribed or modified at or after the time of

discharge on study day will also be presented.

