9.2 Adverse Events

Treatment-emergent AEs are defined as AEs that start or worsen in severity after the first exposure to study medication through the Day 7 visit. Verbatim terms used by investigators to identify AEs in the CRFs will be mapped to the appropriate preferred (PT) and system organ class (SOC) using a standardized coding dictionary (MedDRA Version 21.0 or higher). All coding will be reviewed prior to database lock. All recorded AEs will be listed, but only TEAEs will be summarized.

Statistical Analysis Plan Version: 2.0

Effective Date: 08OCT2018

In addition to a listing of all TEAEs, separate listings of subjects with SAEs and listings of subjects with severe, treatment related, and AEs leading to premature discontinuation will be provided.

An overall summary will be prepared giving for each treatment group, all DFN-15 groups combined and overall of both the number of events and the number of subjects with TEAEs, SAEs, TEAEs by severity, TEAEs by relationship to treatment, and TEAEs leading to premature discontinuation.

The incidence of TEAEs will be summarized for each treatment group by SOC and PT within SOC (sorted in descending order by overall frequency). These summaries will be given in separate tables for the following categories of TEAEs:

- All TEAEs
- TEAEs leading to premature discontinuation
- SAEs

Also summarized will be TEAEs by maximum severity and by maximum relatedness to treatment. Adverse events will be deemed treatment related if they were recorded as probably, possibly, or definitely related.

If a given subject experiences a TEAE that maps to the same PT more than once, the subject will be counted once for the PT at its greatest severity (i.e., mild, moderate, or severe) and causality (i.e., attribution to study medication).

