Duration of an AE will be computed in days (or in hours when duration of the AE is less than 1 day) as the stop date/time of the event minus the start date/time plus 1. If reported as ongoing at the time of database lock, the stop date/time is defined as the date/time of the last visit or the last date/time of any AE for the subject in the database, whichever is later. If an AE is considered resolved, but the stop date is missing, the last day of the month will be imputed if the month and year are available. If only the year is available, and the year is the same as the year of the last visit, the stop date will be the latest of the last visit date or latest AE for the subject in the database. If the year of the AE is prior to the year of the last treatment, the end day and month will be set to 31 December.

For missing or partial start dates, it is most conservative to impute them as temporally related to the first dose of study medication. The following chart will be used to impute start date:

Statistical Analysis Plan Version: 2.0 Effective Date: 08OCT2018

Table 2 Table of Adverse Event Start/End Date/Time Imputation Rules

Missing Portion	Prior to Treatment	Same as Treatment Start Date	After Treatment Start Date
Day	Month and Year < Month and Year of first treatment:	Month and Year = Month and Year of first treatment:	Month and Year > Month and Year of First Treatment:
	Start Day = first day of the month	Start Day = Day of first treatment	Start Day = first day of the month
	Stop Day = last day of the month	Stop Day= last day of the month	Stop Day= last day of the month
Day and Month Define Day as above, then:	Year < Year of first treatment:	Year = Year of first treatment:	Year > Year of first treatment:
	Start Month = July	Start Month =	Month = January
	Stop Month = Dec	Month of first treatment	Stop Month = Dec
		Stop Month = Dec	
Day, Month, and Year	To be conservative, completely missing start dates will be set to the date of first treatment, completely missing end dates will be set to the date of last contact.		
Time	Missing start times will be imputed as 00:01 (or the start time of the first dose administration if AE occurred on the date of first dose administration)		
	Missing stop times will b	e imputed as 23:59	

After following these imputation rules, if the start date is imputed as a date after the end date, the start date will be set to the end date to provide a positive duration for the AE.

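### SAP 9.2 imputes some adverse event onsets to exactly the dose start time but counts as treatment-emergent only events after it, so on a literal reading these events leave the TEAE tables

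*SAP*

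**What the plan says.** SAP 9.2 gives the definition: "Treatment-emergent AEs are defined as AEs that start or worsen in severity after the first exposure to study medication through the Day 7 visit". It then limits the tables: "All recorded AEs will be listed, but only TEAEs will be summarized". Protocol 7.5 draws the same boundary, with an event counting if it "begins or that worsens in severity after at least one dose of study drug has been administered".

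For incomplete onsets, SAP 9.2 states its purpose: "For missing or partial start dates, it is most conservative to impute them as temporally related to the first dose of study medication". Table 2 carries this out:

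- A wholly missing start date becomes the dosing date.
- A missing day in the dosing month becomes the dosing day.
- A missing day and month in the dosing year become the dosing month and day.
- For clock times, "Missing start times will be imputed as 00:01 (or the start time of the first dose administration if AE occurred" on the dosing date).

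A repair rule follows the table: "if the start date is imputed as a date after the end date, the start date will be set to the end date". Its stated aim is a positive duration.

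Two other places bear on the boundary. SAP 6.2 moves events that occurred before treatment into medical history ahead of database lock. SAP 6.3, on concomitant medication, includes the tie explicitly: "Any medication/therapy that stops at or after the date and time of start of treatment".

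**The concern.** SAP 2.2 defines T0 as the start of dosing, so the imputed clock time on the dosing date is T0 itself. A definition that requires onset after exposure does not include an onset at exposure. The imputation is meant to count events of uncertain timing against the drug, yet taken at its word the definition leaves them out of the summaries.

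The boundary matters more here than in most single-dose trials. Check-in, surgery, up to 6 hours of baseline observation and dosing all fall on Day 1. Protocol 6.5.2 to 6.5.4 has adverse events monitored before surgery, between surgery and dosing, and after dosing. Events before and after the dose share a date, so the date alone cannot class a Day 1 event whose time is missing. Adverse event incidence is the first safety endpoint listed in Protocol 8.2.3. Two programmers working from this SAP could produce different TEAE counts from the same data.

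**Working it through.** The plan gives no figure to reproduce. The check applies Table 2 to each pattern of missing onset and compares the result with T0.

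**Inputs.** The TEAE rule and Table 2 are from SAP 9.2, and T0 is from SAP 2.2. The dose time is an assumption for illustration only: 16 July 2018, 11:30. The result depends on ties, not on the time chosen.

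**Step 1: classify.** Let s be the imputed onset. The literal rule is TEAE if s > T0; the alternative is TEAE if s ≥ T0. Later worsening is set aside here.

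| Recorded onset | Imputed onset s | s > T0 | s ≥ T0 |
|---|---|---|---|
| Dosing date, no time | 16 Jul 11:30 | no | yes |
| Dosing month and year, no day or time | 16 Jul 11:30 | no | yes |
| Dosing year only | 16 Jul 11:30 | no | yes |
| Nothing | 16 Jul 11:30 | no | yes |
| Next day, no time | 17 Jul 00:01 | yes | yes |
| Later month, no day or time | 1 Aug 00:01 | yes | yes |
| Earlier month, no day or time | 1 Jun 00:01 | no | no |
| Dosing date, 13:00 recorded | 16 Jul 13:00 | yes | yes |
| Dosing month, no day, 09:00 recorded | 16 Jul 09:00 | no | no |

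Only the first four rows depend on the boundary. They are the patterns that land exactly on T0.

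**Step 2: look for another rule that settles the tie.** SAP 6.2 covers events before treatment, and T0 is not before T0. SAP 9.2 and Protocol 7.5 both say after. No other sentence classifies an onset at T0.

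**Step 3: trace the tables.** All six adverse event shells, 14.3.1.1 to 14.3.1.6, are titled as TEAE tables. An event in the first four rows is listed and, unless it later worsens, enters none of those for which it would otherwise qualify. SAP 9.3 separately promises a summary of serious events and deaths without a TEAE restriction, although the only serious-event shell (14.3.1.4) is for serious TEAEs.

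**Step 4: size.** Take the events that would be TEAEs under s ≥ T0. Let m be the fraction with an incomplete onset, f the fraction of those that land on T0, and w the fraction of these that later worsen. Then

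loss = m × f × (1 − w) ≤ m.

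The documents give none of the three. If m were 2%, 5% or 10% (assumption), the loss would be at most 2%, 5% or 10%. It reaches those values only if f = 1 and w = 0.

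**Step 5: check the opposite error.** Suppose the definition becomes s ≥ T0 and nothing else changes. Take a dose at 13:00 and a Day 1 event that stopped at 11:00 with no start time (times assumed). Table 2 gives a start of 13:00. Start and stop share a date, so a repair that compares dates does not act. The SAP's hourly duration, stop minus start plus 1, is (11 − 13) + 1 = −1 h. The event would be flagged as a TEAE although it ended before the dose. Correcting the boundary alone is therefore not quite enough.

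**The case against.** The strongest reply is that the intent is plain. The SAP says it imputes towards the dose in order to be conservative, and reading its definition as a strict inequality defeats the only stated purpose of the rule. A sensible programmer may well include the tie. This stands to the extent that no data have been shown to be lost. It does not remove the conflict, because the two written rules still give the opposite of the stated purpose, and SAP 6.3 shows that the authors write the tie in when they mean to include it.

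Three stronger readings are tempting and are not supported:

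- **That the loss equals the rate of missing onsets.** Events with a known later date or a later month stay treatment-emergent under Table 2, as Step 1 shows, and an event at T0 that later worsens still counts.
- **That every safety summary loses these events.** SAP 9.3 summarises serious events and deaths without a TEAE limit. An ordinary event would not in any case belong in the tables for discontinuations or serious events.
- **That a pre-dose Day 1 event would certainly be miscounted once the tie is included.** SAP 6.2 should send an event known to have stopped before dosing to medical history. The repair rule can also be read as acting on date and time, since Table 2 is titled for both and the aim is a positive duration. The wording leaves this open rather than wrong.

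It is also fair that Day 1 events with a recorded time are unaffected, and that the protocol plans no statistical testing of safety.

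**Conclusion.** The point holds as a conflict between two stated rules in SAP 9.2. Four patterns of missing onset are imputed to exactly T0. Read literally, those events are neither treatment-emergent nor pre-treatment, and unless they later worsen they appear in listings but not in Tables 14.3.1.1 to 14.3.1.6. This contradicts the SAP's own conservative aim.

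The conclusion rests on reading after as strictly later than T0, and on the clock time being missing as well as any part of the date. The number of events affected cannot be estimated from the documents and may be small. The defect is worth correcting because it makes the TEAE count depend on a programmer's choice.

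**What to change.** Make three edits to the SAP before unblinding:

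1. In 9.2, define a TEAE as an adverse event that starts or worsens at or after the start of study drug administration (T0), through the Day 7 visit. This matches the boundary already used in SAP 6.3.
2. In Table 2, impute an onset to T0 only if the recorded stop date/time is missing or is at or after T0. An event that stopped before T0 is handled as pre-treatment, consistent with SAP 6.2.
3. Apply the repair for a start later than the stop to date and time together, not to the date alone.

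The cost is a few sentences and a small programming change, with no new data. The TEAE count may be slightly higher, which is the direction the SAP says it wants.

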9.3 Deaths, Serious Adverse events, and Other Significant Adverse Events

A serious adverse event (SAE) is defined as an event that may constitute a significant medical hazard or side effect, regardless of the investigator or sponsor's opinion about its relationship to study material. Serious events include, but may not be limited to, any event that:

Is fatal

 Is life-threatening (places the subject at immediate risk of death while the event is occurring)

Statistical Analysis Plan Version: 2.0

Effective Date: 08OCT2018

- Requires inpatient hospitalization or prolongs hospitalization
- Results in persistent or significant disability/incapacity
- Is a congenital anomaly/birth defect

Significant untoward medical events that may not be life-threatening or result in death or hospitalization, or events that require intervention to prevent one of the outcomes listed above or that result in urgent investigation, may be considered serious. Elective hospitalizations for conditions that existed before administration of study material are not to be considered SAEs. Serious adverse events and deaths will be listed and summarized separately for the safety population.

9.4 Clinical Laboratory Evaluation

Clinical laboratory samples will be collected at screening, Day 1 at the time of discharge, and EOS (as applicable). For continuous laboratory parameters, the observed values and changes from baseline will be summarized at each scheduled visit, overall and for each treatment group. For categorical laboratory parameters, frequency counts and percentages of subjects in each category will be provided.

Laboratory test results will be displayed in by-subject listings, and values outside of the normal reference range will be flagged.

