### **8.2.3. Safety Endpoints**

The safety endpoints will include the following:

- 1) incidence of AE's and SAEs
- 2) incidence of abnormal clinical laboratory tests, including routine blood chemistry and hematology, coagulation parameters and urinalysis
- 3) incidence of clinically significant changes in vital signs parameters
- 4) incidence of clinically significant abnormal ECG findings

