Assessments	Screening	Day 1			Day 1 Treatment Period (0H = time of dosing)														Dis-charge	EOS
	Day -28 to Day -1	Check-in / Prior to Surgery	Surgery	Pre-Dose Baseline	0H	15 min	30 min	45 min	1H	1.5H	2H	2.5H	3H	4H	5H	6H	7H	8H		
AE assessment	←																		→	
Record rescue medication use					←													→		
AE monitoring					←													→		
Record concomitant medications	←																	→		

- a) Assess updates since screening and evaluate for continued eligibility.
- b) Subject will be randomized if all I/E criteria are met, including post-operative inclusion criteria.
- c) Vitals include systolic and diastolic (seated) blood pressure, pulse rate and respiratory rate, seated or supine. To be completed prior to early withdrawal, prior to pain assessments, when applicable.
- d) Clinical laboratory evaluations will be performed according to the schedule in Appendix C. Any of the above laboratory parameters (or any additional laboratory parameter not part of the clinical lab evaluation) may be assessed unscheduled based on the discretion of the investigator during the study, and may be assessed during the study after consultation with the study Medical Monitor, unless needed in emergency to ensure the safety of the subject; in such a case, Medical Monitor should be notified as soon as possible.
- e) Day 7, End of study follow-up safety lab draws are to be performed only if there is a clinically significant abnormality or ongoing AE(s).
- f) Urine pregnancy test will be performed for all female subjects of child-bearing potential at Screening, Prior to Surgery and Randomization and at End of Study.
- g) Urine screen for common drugs of abuse and alcohol breathalyzer test will be performed for all subjects at screening, and prior to admission for surgery (Check-in).
- h) For timepoints where ECG coincides with vital signs collection, ECG must be conducted first or concurrently with vital signs. Should pain assessments and PK/ safety lab samples also coincide, ECG and vitals must precede applicable pain assessments, then PK and safety lab draws are to follow pain assessments; see item (l). To be completed prior to early withdrawal, when applicable.
- i) Pre-dose assessments only; determines randomization if “moderate” to “severe” baseline pain outcome (PI) and NPRS score  $\geq 5$ .

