9.0 Safety Evaluation

9.1 Overview of Safety Analysis Methods

All safety outcomes will be summarized using the safety population. Safety outcomes include:

- Incidence of treatment-emergent AEs (TEAEs)
- Changes from baseline in clinical laboratory test results

- Changes from baseline in vital sign measurements
- Changes from baseline in physical examinations.
- Changes from baseline in ECG findings,
- Evaluation of surgical wound healing.

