9.5 Vital Signs, Physical Measurements, and Physical Examinations

9.5.1 Vital Signs and Physical Measurements

Vital signs will be collected at screening, Day 1 prior to surgery, at pre-dose baseline, and then at 1, 2, 4 and 8 hours after the administration of study medication, or at the time of early discontinuation, and at the end of study visit on Day 7 (± 3 days).

Observed values and changes from baseline will be summarized using mean and change-from-baseline descriptive statistics, overall and for each treatment group, for the following measurements: systolic blood pressure (mmHg), diastolic blood pressure (mmHg), heart rate (beats/minute), and respiratory rate (breaths/minute).

Body weight and height will be measured, and BMI will be calculated during the screening visit only. These values will be summarized along with other baseline characteristics. Vital signs will be displayed in a by-subject listing.

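### Laboratory and vital-sign safety endpoints are defined as incidences but planned only as descriptive summaries, and end-of-study lab summaries rest on a subset selected after treatment

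*SAP*

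**What the plan says.** Protocol 8.2.3 words the laboratory endpoint as "incidence of abnormal clinical laboratory tests, including routine blood chemistry and hematology, coagulation parameters and urinalysis" and the vital-sign endpoint as "incidence of clinically significant changes in vital signs parameters". Both are counts of subjects or findings, not averages.

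The analysis text is different. SAP 9.1 restates the laboratory outcome as "Changes from baseline in clinical laboratory test results" and does the same for vital signs. SAP 9.4 then specifies: "For continuous laboratory parameters, the observed values and changes from baseline will be summarized at each scheduled visit, overall and for each treatment group". Out-of-range laboratory results appear only in by-subject listings, where "values outside of the normal reference range will be flagged". For vital signs, SAP 9.5.1 specifies: "Observed values and changes from baseline will be summarized using mean and change-from-baseline descriptive statistics, overall and for each treatment group". SAP 3.0 defines the descriptive set as n, mean, median, SD, minimum and maximum.

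The table list in SAP 15.1 matches this. Tables 14.3.2.1 to 14.3.2.4 (chemistry, hematology, coagulation, continuous urinalysis) and 14.3.3 (vital signs) hold results and changes. Table 14.3.2.5 counts categorical urinalysis results. The ECG, the fourth endpoint in Protocol 8.2.3, has a shift table (14.3.4).

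SAP 9.4 lists end of study, qualified as applicable, among the laboratory collection times. Protocol 6.4.1, Appendix A (footnote e) and SAP 2.2 limit end-of-study draws to subjects with a clinically significant abnormality or an ongoing adverse event.

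**The concern.** Two named safety endpoints have no analysis that yields them. A reader of the study report could not find, by dose, how many subjects moved outside the reference range for creatinine, platelets or prothrombin time, or how many had a notable change in blood pressure. Safety and tolerability is the secondary objective (Protocol 2), and the exclusion criteria single out thrombovascular risk, renal insufficiency and coagulation disorders. In a single-dose study with small arms, harm of that kind is more likely to appear as a few displaced subjects than as a shift of the arm mean.

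The end-of-study rows raise a separate problem. Membership of that subset depends on what happened after dosing and may differ by arm. A mean printed next to the Discharge mean invites a comparison that the data cannot support.

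**Working it through.** The documents state no figure to reproduce. The main check sets endpoint against analysis; the arithmetic after it only gives scale.

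**Endpoint against planned output**

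| Protocol 8.2.3 endpoint | Planned by-arm output | Incidence by arm? |
|---|---|---|
| Abnormal chemistry, hematology, coagulation | Tables 14.3.2.1 to 14.3.2.3: values and changes; flags in listings | No, except findings reported as adverse events |
| Abnormal urinalysis | Table 14.3.2.4 (continuous), Table 14.3.2.5 (categorical) | Category counts only for categorical parameters |
| Clinically significant vital-sign changes | Table 14.3.3: values and changes; no criterion given | No, except findings reported as adverse events |
| Clinically significant abnormal ECG | Table 14.3.4: shift table | Yes, category counts |

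**Sensitivity of a mean to a few subjects**

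Input: 120 subjects randomized 1:1:1:1 (Protocol 8.1 and 5.5), so 120 / 4 = 30 per arm. The displacements are assumptions.

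- Standard error of an arm mean: 1/√30 = 0.18 SD. Standard error of a difference between two arms: √(2/30) = 0.26 SD.
- Shift of the arm mean when k subjects are displaced by s SD: k × s / 30.
- One subject: 1 × 3 / 30 = 0.10 SD and 1 × 5 / 30 = 0.17 SD, both below 0.18 SD.
- Two subjects: 2 × 3 / 30 = 0.20 SD, below the 0.26 SD for a difference; 2 × 5 / 30 = 0.33 SD, above it.
- In pressure units, if two subjects rise by 40 mmHg: 2 × 40 / 30 = 2.7 mmHg in the mean, against an incidence of 2/30 = 6.7%.

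**Whether the maximum replaces a count**

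Suppose each subject has a 5% chance of exceeding an upper limit. The chance that at least one of 30 does is 1 − 0.95^30 = 0.79; at 10% it is 1 − 0.90^30 = 0.96. The maximum would then usually lie above the limit in every arm, and it does not distinguish one such subject from several.

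**What an end-of-study mean could represent**

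Assume one normally distributed analyte, with draws triggered only by exceeding an upper limit c. The mean of the selected subjects at selection is φ(c) / (1 − Φ(c)).

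- c = 1.645 (upper 5%): 0.1031 / 0.0500 = 2.06 SD above the population mean. Expected number 120 × 0.05 = 6, or 1.5 per arm.
- c = 1.96 (upper 2.5%): 0.0584 / 0.0250 = 2.34 SD. Expected number 120 × 0.025 = 3, or 0.75 per arm.
- On repeat testing with within-subject correlation 0.5 to 0.8, these means become 0.5 × 2.06 = 1.03 to 0.8 × 2.06 = 1.65 SD, and 0.5 × 2.34 = 1.17 to 0.8 × 2.34 = 1.87 SD.

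The real rule also admits subjects with any ongoing adverse event, whose laboratory values may be normal. That would enlarge the subset and pull its mean back toward the population mean. It would still be a subset defined after treatment.

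**The case against.** A reader might infer that the SAP departed from the protocol's analysis and failed to record this in section 13.0. The documents do not support that. Protocol 8.6.3 and 8.6.4 already call for laboratory and vital-sign values to be summarized by treatment without testing, and the synopsis says the same of all safety parameters. SAP 9.4 and 9.5.1 carry out that text. The mismatch begins inside the protocol, between 8.2.3 and 8.6.3/8.6.4, and the SAP does not repair it.

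A reader might also infer that the plan cannot show clinically significant abnormalities by arm at all. That goes too far. Protocol 7.1 makes laboratory values judged clinically significant reportable as adverse events, and Protocol 7.5 extends this to other examinations. Those arising after dosing reach the by-arm tables of treatment-emergent events. What remains uncounted is narrower: out-of-range continuous laboratory values not judged clinically significant, although the endpoint says abnormal, and vital-sign changes that meet a stated criterion, because none is stated.

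Three more points on the other side stand in part.

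- The summaries include median, minimum and maximum as well as means. In the 40 mmHg example the maximum change would show at least one large rise. It would not show how many.
- The end-of-study row would display its n, the SAP marks it as applicable, and change from baseline uses the same subjects' own baselines. A careful reader could see that it is a subset. The row would still sit in a by-arm table with no note of how its members were chosen.
- It would be wrong to say that every retested subject is abnormal, since an ongoing adverse event is enough for a draw.

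Flagged values can be counted by hand from listings in a study of 120, but that is not a planned analysis of a named endpoint.

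**Conclusion.** The concern holds in limited form. Protocol 8.2.3 promises two incidences, and following the plan yields neither as a by-arm count, apart from categorical urinalysis and whatever is reported as an adverse event. The end-of-study laboratory summaries describe a group selected on events after dosing and should not be read as arm-level results.

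This conclusion rests on the text and the table list. The calculations only illustrate scale: the displacements, the exceedance rates and the correlations are assumptions, not document figures. The consequence is moderate. Safety is descriptive, individual values stay in the listings, and the primary analysis is untouched. The change is worth making because it is cheap and gives a stated endpoint the analysis it lacks.

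**What to change.** 1. **SAP 9.4 and 15.1:** add a low/normal/high shift table from Screening to Discharge for chemistry, hematology and coagulation, with n and % of subjects newly outside the reference range by arm. These are the two occasions on which all subjects are due to be sampled. Surgery falls between them, so active arms should be read against placebo.
2. **SAP 9.4:** show end-of-study laboratory values in listings only, or label them as a selected subset and set them beside the same subjects' discharge values.
3. **SAP 9.5.1 and 15.1:** tabulate by arm the n and % of subjects meeting vital-sign change criteria that the sponsor fixes before unblinding. The criteria must be written down because neither document gives any. No investigator rating of significance is described for vital signs, unlike the ECG (Protocol 6.4.3), so a count built on such a rating may have no data behind it.

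The laboratory and vital-sign values are already collected. The cost is SAP wording, agreement on the vital-sign criteria and about two extra tables.
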